This is a randomized, placebo-controlled, parallel-group, single-center, double-blind trial of vericiguat in subjects with heart failure with reduced ejection fraction (HFrEF) to be conducted in conformance with Good Clinical Practice (GCP).

Purpose

The purpose of this study is to determine the effect of Vericiguat in patients with HFrEF.

This study will:

1) Evaluate the impact of Vericiguat on Peripheral Vascular Function;

- 2) Evaluate the impact of Vericiguat on Patients' Health Status;
- 3) Evaluate the impact of Vericiguat on Inflammation;
- 4) publish and disseminate results.

Primary objective:

1. To determine the impact of Vericiguat administration on vascular function in patients with HFrEF.

Hypothesis: Endothelium-dependent vasodilation, as determined by flow-mediated vasodilation (FMD) testing, will be improved following 12-weeks of Vericiguat treatment compared to placebo.

Secondary objectives:

1. To determine the impact of Vericiguat administration on health-related quality of life and physical capacity in patients with HFrEF.

Hypothesis 1a: Physical capacity, as determined by change in six minute walk test (6MWT) distance, will be better following 12-weeks of Vericiguat treatment compared to placebo.

Hypothesis 1b: Quality of life, as determined by change of Kansas City Cardiomyopathy Questionnaire overall summary score, will be better following 12-weeks of Vericiguat treatment compared to placebo.

2. To explore the relationship between inflammation and vascular function in response to vericiguat in patients with HFrEF.

Hypothesis: A positive correlation between changes in FMD and biomarkers of inflammation will be observed following 12-weeks of Vericiguat treatment, such that the greatest improvements in FMD will be observed in those patients who experience the largest decreases in proinflammatory biomarkers (IL-1β, IL-6, IL-18, and hsCRP).

Study Population

Age of Participants: 18+

Sample Size:

At Utah:

All Centers: 30

Inclusion Criteria:

- 1. History of chronic HF with New York Heart Association (NYHA) Class II-III symptoms. Patients with NYHA 1 (asymptomatic) or NYHA 4 (severe limitations symptoms even while at rest) symptoms, will not be enrolled.
- 2. Left ventricular ejection fraction (LVEF) of ≤45% assessed within 12 months prior to randomization by any imaging method.
- 3. Systemic blood pressure ≥90/60 mmHg.
- 4. Standard guideline-directed HF therapy.

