- 5. If female of reproductive potential, agrees to avoid becoming pregnant while receiving study drug and for 14 days after the last dose of study drug by complying with abstinence from heterosexual activity or use (or have her partner use) contraception during heterosexual activity.

Exclusion Criteria:

1. Addition of a new disease-modifying HF pharmacotherapy or CRT-D in previous 4 weeks.

- 2. Current or anticipated use of long-acting nitrates or nitric oxide (NO) donors including isosorbide dinitrate, isosorbide 5-mononitrate, pentaerythritol tetranitrate, nicorandil or transdermal nitroglycerin (NTG) patch, and molsidomine.
- 3. Current or anticipated use of phosphodiesterase type 5 (PDE5) inhibitors such as vardenafil, tadalafil, and sildenafil.
- 4. Current use or anticipated use of a soluble guanylate cyclase (sGC) stimulator such as riociguat.
- 5. Known allergy or sensitivity to any sGC stimulator.
- 6. Estimated glomerular filtration rate (eGFR) <15 mL/min/1.73 m2 or chronic dialysis.
- 7. Patients who are pregnant or breastfeeding or plan to become pregnant or to breastfeed.

Design

Blinded Trial (Single or Double Blinded)
Placebo Controlled Trial
Randomized Trial

A Randomized Parallel-Group, Placebo-Controlled, Double-Blind, Single - Center Trial of The Effect of Vericiguat on Peripheral Vascular Function, Patient Health Status and Inflammation in Patients with Heart Failure with Reduced Ejection Fraction.

Study Procedures

Recruitment/Participant Identification Process:

Potential participants will be screened while admitted inpatients at the University and VA Hospitals or while attending routine clinic appointments in the Cardiovascular Medicine clinic.

Clinicians will explain to eligible patients the purpose of the study, study interventions and evaluations, and the potential risks and benefits of participation, and will answer any questions. If a patient agrees to participate in the study, they will review and sign the IRB approved informed consent form before any study specific procedures are conducted.

Informed Consent:

Description of location(s) where consent will be obtained:

University of Utah Health Sciences Center Veterans Affairs SLC Health Care System (VAMC)

Description of the consent process(es), including the timing of consent:

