Subjects will be directed to bring any used and unused bottles to each visit. The investigator must maintain a complete and current accountability record for the blinded investigational product.

Study drug will be dispensed starting at Randomization Visit and at Visit 1. Compliance with blinded trial medication will be assessed by tablet counts of returned medication. To facilitate this, subjects must be instructed to return all of the study drug packaging including unused study drug and empty packaging.

Any discrepancies between actual and expected amount of returned study medication must be discussed with the subject at the time of the visit, and any explanation must be documented in the source records.

Consultation should occur in a timely manner upon site learning of poor study drug compliance. The research site should conduct patient counseling regarding importance of study drug adherence, and the investigator can dispense study drug after such counseling, if in their medical judgment, the patient is able to comply moving forward with study treatment instructions.

Clinical Procedures/Assessments

Height

Height will be measured without shoes, using a stadiometer or other appropriate device.

Weight

Body weight will be measured using a standardized scale at each of the pre-defined time points outlined in the Trial Flow Chart.

Physical Examinations

Physical examination will be done at a clinical visit (inpatient or outpatients) preceding screening or randomization. The documentation will be reviewed by the investigator or qualified designee.

Vital Signs

Vital sign measurements include a triplicate measurement of sitting blood pressure and pulse rate. Site personnel should use the same blood pressure measuring device throughout the study for each subject. Other procedures should not be performed during the time of the blood pressure and pulse rate measurements.

Blood pressure assessment is to be completed after the subject has been seated for a 10 - minute rest. Whenever possible, BP measurements should be obtained using the same arm, same BP monitoring device, and same examiner at each visit. Systolic and diastolic blood pressures will be determined by averaging 3 replicate measurements obtained approximately 2 minutes apart.

Pulse Rate

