Pulse rate is to be assessed after the subject has been seated for a 10 minute rest. Three measurements of the pulse rate must will be taken determined by averaging 3 replicate measurements obtained approximately 2 minutes apart.

Assessment of pulse rate can be manual (rather than using an automated device); however, when done manually, pulse rate must be measured in the brachial/radial artery for at least 30 seconds.

Quality of Life Measures

Kansas City Cardiomyopathy Questionnaire

The KCCQ-12 is a 12-item, self-administered questionnaire intended for the quantification of HF patients' perspectives of how their disease impacts their lives. The questionnaire requires, on average, 5 to 8 minutes for completion. The KCCQ-12 measures the impact of patients' heart failure, or its treatment, on 7 distinct domains using a 2-week recall period: symptom frequency, symptom burden, physical limitation, health perceptions, social limitations, self-efficacy and symptom stability. The KCCQ-12 domains of self-efficacy and symptom stability will be reported but are not considered in the efficacy assessment as they address patient knowledge and recent changes in symptoms respectively.

In addition, there are 3 summary scores; a total symptom scale that combines the symptom frequency and the symptom burden scores, a clinical summary scale that combines the total frequency and physical limitation scores to replicate the NYHA Classification, and an overall summary score that includes the Total Symptom, PhysicalLimitation, Social Limitation and Quality of Life scores. The clinical summary score and its components address the most relevant concepts for the heart failure patients, showing good correlation with improvement following HF hospitalization.

Visual Analogue Scale

The VAS records patient self-rated health on a 20 cm vertical VAS with endpoints labeled 'the best health you can imagine' and 'the worst health you can imagine' and is scored on a 0 to 100 scale.

Vital Status Assessment

Vital status is collected at Week 2, Week 8 and Final Phone Contact. This assessment can also be performed at any point in the trial when vital status is in question, unless subject has specifically withdrawn consent for further follow-up.

Laboratory Procedures/Assessments

Details regarding specific laboratory procedures/assessments to be performed in this trial are provided below.

Laboratory tests are specified in Table 2.

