Six-minute walk test distance will be performed according to published guidelines for this patient group by trained research staff. The 6MWT will be performed indoors, along a flat, straight corridor with a hard surface. The subjects will wear comfortable clothing and shoes. The subjects will be instructed on the objectives of the test and be provided instructions on how the test will be carried out.

Cardiac and Inflammation Marker Investigations

Cardiac and inflammation marker investigations will examine the impact of vericiguat on HF and peripheral vascular disease progression and identify candidate markers that may predict drug response to the treatment.

Marker blood samples will be collected at the time points indicated in Study Flow Chart.

Investigators will not receive the results of analyses during the study, and no alerts will be sent.

Other Procedures

Withdrawal/Discontinuation

Subjects who discontinue/withdraw from treatment prior to completion of the treatment regimen should be encouraged to continue to be followed for all remaining study visits.

When a subject discontinues/withdraws from participation in the trial, all applicable activities scheduled for the Premature Treatment Discontinuation visit should be performed at the time

of discontinuation. Any adverse events which are present at the time of discontinuation/withdrawal should be followed in accordance with the safety requirements.

Blinding/Unblinding

STUDY TREATMENT IDENTIFICATION INFORMATION IS TO BE UNMASKED ONLY IF NECESSARY FOR THE WELFARE OF THE SUBJECT. EVERY EFFORT SHOULD BE MADE NOT TO UNBLIND THE SUBJECT UNLESS NECESSARY.

For emergency situations where the investigator or sub-investigator needs to identify the drug used by a subject and/or the dosage administered he/she will contact the investigational pharmacy and make a request for emergency unblinding. The investigator or sub-investigator will enter the intensity of the adverse experiences observed, their relation to study drug, the reason thereof, etc., in the medical chart.

Visit Requirements

Visit requirements are outlined in Trial Flow Chart.

Screening

Procedures for the Screening visit can be performed over several days. Alternatively, the screening visit and randomization visit can take place on the same day and subjects can be randomized during this visit if all required tests for eligibility criteria are available.

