Additionally, evidence of a LVEF <45% within 12 months prior to randomization by any method (most recent measurement must be used) must be provided.

Subjects who sign the ICF and, who for any reason (e.g. failure to satisfy the selection criteria), do not continue on to randomization will be considered a screen failure.

Treatment Period

Visit requirements are outlined in Trial Flow Chart. Total treatment period will be 12 weeks.

Randomization Visit

At the randomization visit, subjects who fulfill all inclusion/exclusion criteria will be randomized to either vericiguat or placebo on a background of standard of care HF treatment.

As noted above, the Screening visit and the Randomization visit can occur on the same day, if all required tests for eligibility criteria are available at screening visit.

All procedures and assessments specified for this visit will be done after screening visit procedures are performed.

Eligible subjects will be provided a blood pressure machine and cuff to perform at-home blood pressure assessment required at FU phone call A (performed at week 2) and FU phone call B (performed at week 8).

Unscheduled Visits

In the event a subject requires an unscheduled visit for dose modification, the following assessments will be performed:

- Adverse events
- Dose assessment
- Clinical events
- Concomitant medication: record any new or ongoing medication or changes in dosage
- Blood pressure and pulse rate (3 measurements, each approximately 2 minutes apart) prior to study drug dosing

Upon interruption of the study drug due to intolerability, intake should be resumed as soon as medically justified to the discretion of the investigator.

Investigators should make every attempt to resume study drug treatment in all subjects after interruption of study drug as soon as medically justified.

Follow-Up Phone Calls

Patients will be contacted at specific timepoints mentioned in study Flow Chart to assess for clinical events, adverse events, blood pressure measurements and vital status (if applicable) and titrate the investigational drug doses accordingly.

Final Visit

Final Visit's study procedures are outlined in Study Flow Chart.

Final Phone Contact

All subjects will be contacted by phone after 14 days of the Final visit to assess for clinical events, adverse events and vital status (if applicable).

Procedures performed for research purposes only:

Statistical Methods, Data Analysis and Interpretation

Statistical Methods

General

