Standard descriptive statistics (proportions and frequencies for categorical factors; means, standard deviations, and designated percentiles for numeric factors) will display baseline characteristics by randomized treatment group. If a substantial imbalance is identified in a particular baseline factor, the ITT analyses described below will be accompanied by sensitivity analyses to investigate the impact of inclusion of this factor as a covariate. Outcomes with substantial skewness may be transformed prior to subsequent analyses to better approximate normality. Analyses evaluating the effect of the treatment on study outcomes will be performed in accordance with the intention-to-treat principle, with subjects analyzed according to their randomly assigned treatment irrespective of the achieved dose of Vericiguat. Unless specified otherwise, hypothesis tests will be performed with 2-sided α =0.05, without adjustment for multiple comparisons.

Primary Analysis

The effect of administration of Vericiguat on the primary FMD outcome will be estimated by applying an analysis of covariance to compare the mean FMD levels at 12 weeks between the Vericiguat and placebo groups, with the baseline FMD levels included in the model as a covariate.

Secondary Analyses

The effect of administration of Vericiguat on the secondary 6-minute walk test and KCCQ outcomes will be estimated by applying separate analyses of covariance to compare the mean levels of these outcomes at 12 weeks between the Vericiguat and placebo groups, with the baseline level of the outcome included as a covariate. Separate analysis of covariance models will also be used to estimate the effects of the intervention on C-Reactive Protein and Interleukinç 1β , 6, 18. If these markers exhibit heavy positive skewness, as we expect, they will be log transformed prior to analysis.

We will also provide scatter plots with Pearson and Spearman partial correlations with adjustment for randomized treatment group to describe the association of the change in FMD from baseline to 12 weeks with changes in individual inflammatory markers during the same time interval. We will also provide Pearson and Spearman correlations relating changes in FMD to changes in inflammatory markers separately within the two randomized groups. Positively skewed inflammatory markers will be log transformed prior to this analysis.

Power analyses

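### Inpatient baselines are permitted and enrolment setting is not adjusted for, so recovery shared by both arms could produce the FMD-inflammation correlation that Objective 2 predicts

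*Combined protocol and SAP*

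**What the plan says.** - **Recruitment/Participant Identification Process:** "Potential participants will be screened while admitted inpatients at the University and VA Hospitals", or at routine cardiovascular clinic appointments. The consent section repeats this.
- **Physical Examinations:** "Physical examination will be done at a clinical visit (inpatient or outpatients) preceding screening or randomization".
- **Visit Requirements, Screening:** procedures may be spread over several days; alternatively "the screening visit and randomization visit can take place on the same day and subjects can be randomized during this visit", provided the eligibility results are available.
- **Eligibility:** the nearest safeguards are Inclusion 1, "History of chronic HF with New York Heart Association (NYHA) Class II-III symptoms" (Class 1 and Class 4 are not enrolled), and Exclusion 1, "Addition of a new disease-modifying HF pharmacotherapy or CRT-D in previous 4 weeks". Nothing addresses a current or recent admission, decompensation or acute illness.
- **Treatment Period:** "Total treatment period will be 12 weeks".
- **Secondary Analyses:** scatter plots with "Pearson and Spearman partial correlations with adjustment for randomized treatment group to describe the association of the change in FMD" with changes in individual inflammatory markers, plus unadjusted correlations within each randomised group.
- **Statistical Methods, General:** a baseline factor that is substantially imbalanced between the arms is added as a covariate in sensitivity analyses of the ITT comparisons.
- **Correlational analyses:** 20 evaluable subjects are said to give 80% power for a partial correlation of 0.59.

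**The concern.** Objective 2 predicts that FMD improves most in patients whose inflammatory markers fall most, and presents this as a response to vericiguat. A patient measured during an acute illness may start with low FMD and high markers and move towards usual values over 12 weeks on either treatment. A stable clinic patient would not. Mixing the two creates a negative correlation between the signed changes within each arm, which is the predicted direction.

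Randomisation does not guard against this, because the correlation is an association among patients within arms and not a contrast between arms. Adjusting for arm removes only the difference in mean change between the arms. At stake is the interpretation of a secondary objective that has its own hypothesis and its own power statement.

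**Working it through.** **Inputs from the plan.** 20 evaluable patients (10 per arm); SD of FMD 2.4%; SD of log hsCRP 1.323, also assumed for the interleukins; serial correlation 0.5 (the plan's scenario for FMD); two-sided 5% tests.

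**Assumptions, because the documents give no values.** Inpatient share q of 25% or 50%. Inpatients recover by d SDs on both FMD (up) and log marker (down), in both arms. There is no drug effect and no true FMD-marker link within a setting. The serial correlation of 0.5 is applied to the markers as well.

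**1. The plan's detectable correlation.** By Fisher's z, r = tanh[(1.960 + 0.842)/√(20 − 3 − k)], where k is the number of covariates.
- k = 0: tanh(2.802/√17) = 0.591, which matches the stated 0.59.
- k = 1 (arm): tanh(2.802/√16) = 0.605.
- k = 2 (arm and setting): tanh(2.802/√15) = 0.619.

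**2. Correlation induced by shared recovery.** At serial correlation 0.5 the SD of a change equals the SD of a single value, since √[2(1 − 0.5)] = 1. With v = q(1 − q)d², the covariance of the two changes is −v and each variance is 1 + v, so r = −v/(1 + v). Example: q = 0.5 and d = 1.5 give v = 0.5625 and r = −0.36.

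**3. False-positive rate of the arm-adjusted partial correlation** (simulation, n = 20, nominal 5%). The last column translates d into the plan's units: 2.4d points of FMD, and a marker fall of 1 − exp(−1.323d).

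| d | r, q = 25% | false positives | r, q = 50% | false positives | d in plan units |
|---|---|---|---|---|---|
| 0.5 | −0.04 | 5.2% | −0.06 | 5.4% | 1.2 points; 48% fall |
| 1 | −0.16 | 10% | −0.20 | 13% | 2.4 points; 73% fall |
| 1.5 | −0.30 | 24% | −0.36 | 33% | 3.6 points; 86% fall |
| 2 | −0.43 | 47% | −0.50 | 65% | 4.8 points; 93% fall |

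If the serial correlation is 0.7, the same recovery does more: at q = 50% the rate is 23% for d = 1 and 91% for d = 2.

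**4. With setting added as a second covariate,** the rate returns to about 5% in every scenario (0.049 to 0.052). The simulation gives every inpatient the same mean recovery. If recovery varied among inpatients and moved FMD and markers together, part of the induced correlation would remain after adjustment.

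**5. The placebo-arm correlation as a check.** With 10 patients, a correlation needs to be about 0.76 (t-test simulation) to 0.79 (Fisher) for 80% power. To separate the two arms, the SE of the difference in z is √(2/7) = 0.535, and 2.802 × 0.535 = 1.498. That corresponds to r = 0.90 in one arm against 0 in the other.

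**6. The primary FMD ANCOVA.** With full recovery by week 12, the residual variance relative to the FMD variance is 1 − 0.25/(1 + v), against 0.75 without recovery.
- q = 25%: the residual SD rises 2.6% (d = 1) to 6.9% (d = 2).
- q = 50%: it rises 3.3% (d = 1) to 8.0% (d = 2).

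In simulation at q = 50%, power at a 2.76% difference falls from 0.77 to 0.74 (d = 1) and 0.71 (d = 2). At the hypothesised 5.1% it stays at or above 0.99. The treatment estimate is unbiased and type I error stays near 5%.

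**The case against.** **An inpatient baseline is not stated.** The text says only that inpatients are screened. Screening may take several days, same-day randomisation is an option, and the flow chart that would place baseline FMD and blood sampling is not shown. No sentence says that those admitted have an acute cardiac or inflammatory episode, and Class 4 patients are excluded. This stands: the exposure is permitted, not established.

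**The size is assumed.** At 0.5 SD the effect is negligible. At 2 SD the spontaneous FMD gain of 4.8 points nearly equals the whole hypothesised drug effect of 5.1%, and the same d is imposed on FMD and marker. This also stands, so the upper rows of the table show sensitivity and are not a forecast.

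**Safeguards exist.** The within-arm correlations are the natural control, since shared recovery should appear on placebo too. They help, but 10 patients make them a weak control. The imbalance-triggered sensitivity analysis concerns differences between arms in the ITT comparisons. It would not detect recovery common to both arms and does not reach the correlations.

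**The analysis is exploratory.** The objective is framed as exploring a relationship, and the power section calls the secondary analyses exploratory. A correlation between two changes would not establish mechanism even in stable outpatients. This stands and sets the severity.

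**A stronger reading to avoid.** A reader might infer that a mixed population also undermines the primary result, or adds serious noise to it. The documents do not support that. Growth in the SD of change scores (√1.25 = 1.12, or 12%, at q = 50% and d = 1) is not the relevant measure, because the plan analyses 12-week values adjusted for baseline. In that model the loss is the few per cent shown in step 6, and randomisation against placebo keeps the contrast unbiased. Extra noise in 6MWT and KCCQ was not quantified, and no claim is made about it.

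**Conclusion.** The point holds for Objective 2 only, and is minor. As written, the plan allows recovering inpatients and stable outpatients to be pooled in a correlation adjusted for arm alone, and recovery shared by both arms can then imitate the predicted finding. The rise in false positives is negligible for a recovery of 0.5 SD, about double the nominal rate or a little more at 1 SD, and serious from 1.5 SD. These figures rest on an assumed inpatient share of 25% to 50%, equal standardised recovery in FMD and marker, and a serial correlation of 0.5. If no baseline is taken during an admission or acute illness, this problem does not arise. The primary FMD comparison is not called into question.

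**What to change.** 1. Record for every patient whether baseline measurements were taken as an inpatient or an outpatient. Do this prospectively, since it may be hard to reconstruct later.
2. In Secondary Analyses, adjust the pooled Pearson and Spearman partial correlations for arm and enrolment setting.
3. State that the placebo-arm correlation will be reported as a control when the vericiguat-arm correlation is interpreted, with a note on its low precision at about 10 patients.

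**Cost:** one data field and one degree of freedom. The detectable partial correlation moves from about 0.605 to about 0.62.

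Taking baseline only after discharge and a stable period would deal with the problem at source. It would also delay enrolment and might narrow the range of inflammatory states that the study wants to examine. Whether to require it, and for how long, is a clinical choice for the sponsor.

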NT-proBNP, TNF- α , hsCRP, IL-1 β , IL-6, IL-18 measurements assessed by the central lab will be blinded after Visit 2.

Table 2. Laboratory Tests

Hematology Chemistry
Other

Hematocrit

(Hct) Bicarbonate Natriuretic

Peptide (NTproBNP)

Hemoglobin (Hb) Blood

glucose Serum β-human chorionicgonadotropin†

Mean corpuscular volume(MCV)

Blood urea nitrogen

(BUN) TNF-α

Mean corpuscular hemoglobin

(MCH) Calcium hsCRP

Mean corpuscularhemoglobin

concentration(MCHC) Creatinine IL-1\beta

Platelet

count Chloride IL-6

Red blood cells (RBC) Potassium

(K) IL-18

Red cell distribution width(RDW) Sodium (Na)

Reticulocytes

White blood cells (WBC)

Flow Mediated Dilation (FMD)

A blood pressure cuff will be placed on the arm, distal to the ultrasound Doppler probe on the brachial artery. Simultaneous measurements of brachial artery blood velocity and vessel diameter will be performed using a linear array transducer operating in duplex mode, with an imaging frequency of 14 MHz and Doppler frequency of 5 MHz (Logic 7, GE Medical Systems, Milwaukee, WI). All measurements will be obtained with the probe appropriately positioned to maintain an insonation angle of 60° or less. The sample volume will be maximized according to vessel size and centered within the vessel on the basis of real-time ultrasound visualization. The brachial artery will be insonated approximately midway between the antecubital and axillary regions, and measurements of diameter and blood velocity (Vmean) will be obtained continuously at rest and for 2 minutes after cuff deflation. Enddiastolic, ECG R-wave-gated images will be collected via video output from the Logic 7 for off-line analysis of brachial artery vasodilation using automated edge-detection software (Medical Imaging Applications, Coralville, IA). During FMD, non-invasive arterial blood pressure may be assessed. Systemic arterial blood pressure (ABP) will be measured noninvasively on a continuous basis using finger photoplethysmography (Finometer, Ohmeda, Madison, WI, USA). The finometer cuff will be placed on a finger and supported at heart level.

6 MWT (Six-minute walk test)

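### Does blinding six laboratory markers only "measurements assessed by the central lab will be blinded after Visit 2" leave earlier results open to investigators in a double-blind trial?

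*Combined protocol and SAP*

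**What the plan says.** All references are to the combined protocol and SAP.

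- **Laboratory Procedures/Assessments**, just before Table 2: NT-proBNP, TNF-α, hsCRP, IL-1β, IL-6 and IL-18 "measurements assessed by the central lab will be blinded after Visit 2".
- **Cardiac and Inflammation Marker Investigations**: "Investigators will not receive the results of analyses during the study, and no alerts will be sent". No visit limit is attached. On timing, the section says only "Marker blood samples will be collected at the time points indicated in Study Flow Chart".
- **Trial Compliance**: "Study drug will be dispensed starting at Randomization Visit and at Visit 1". This is the only visible text that helps to place the numbered visits.
- **Final Phone Contact**, the last scheduled step: "All subjects will be contacted by phone after 14 days of the Final visit to assess for clinical events, adverse events and vital status".
- **Secondary Analyses**: "Separate analysis of covariance models will also be used to estimate the effects of the intervention on C-Reactive Protein" and on the three interleukins. The correlation analysis relates the "change in FMD from baseline to 12 weeks with changes in individual inflammatory markers during the same time interval".
- **Power analyses**: 24 subjects randomized and 20 evaluable. TNF-α is powered alongside the interleukins. Secondary outcomes are declared exploratory.

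**The concern.** The two blinding statements differ in scope: one has a start point and the other has none. A start point normally implies that something before it is handled differently. Dispensing happens at randomization and again at Visit 1, so Visit 2 appears to come after randomization, and results obtained up to then could include on-treatment values. If Visit 2 is the final visit, only a phone call is scheduled afterwards, and the laboratory sentence would blind no scheduled sample.

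The laboratory sentence is also the one that names the central lab and the analytes, so a laboratory might take its reporting rule from there. The Background reports that hsCRP fell significantly after 12 weeks of vericiguat, so an on-treatment value could hint at the assigned arm. At stake would be the blind of a double-blind trial, with possible influence on effort-dependent or self-reported outcomes (6MWT, KCCQ), on adverse-event reporting, or on the reading of the FMD images.

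**Working it through.** The plan gives no figure to reproduce. The check compares the two sentences and then counts what could be exposed.

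**Step 1. Do the sentences contradict each other?** Call the laboratory sentence L and the marker-section sentence M.

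| | Results up to Visit 2 | Results after Visit 2 |
|---|---|---|
| L | silent | blinded |
| M | not given to investigators | not given to investigators |
| L and M together | not given to investigators | blinded |

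L is silent about the earlier period; it does not order release. Withholding all results meets both sentences, and releasing any result to investigators during the study breaches M. The pair therefore yields one workable rule, the stricter one.

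**Step 2. Do they cover the same results?** M names no analyte. Its heading covers cardiac and inflammation markers. Among the tests in Table 2, NT-proBNP fits the first description and the other five fit the second. The documents name no other markers of that kind, so treating the sets as the same is reasonable, though it is an inference.

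**Step 3. Does anything in the plan need early release?** No inclusion or exclusion criterion uses any of the six markers. The listed marker analyses use baseline and 12-week values only.

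**Step 4. How many on-treatment results would be open if L were applied alone?** Assumption: markers are drawn at baseline and week 12 only, as the analyses suggest. The formula is subjects × on-treatment draws up to and including Visit 2 × markers.

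- *Visit 2 before the final visit*: 20 × 0 × 6 = 0. Only baseline values are open.
- *Visit 2 is the randomization visit* (not supported by Trial Compliance): 20 × 0 × 6 = 0.
- *Visit 2 is the final visit*: 20 × 1 × 6 = 120, or 24 × 1 × 6 = 144 if every randomized subject gives a final sample. Of the 120, 20 × 4 = 80 concern the markers analysed under Secondary Analyses, and 20 × 5 = 100 concern those powered as outcomes (the same four plus TNF-α).

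An extra on-treatment draw at or before Visit 2 would add up to 120 results (144 for all randomized subjects). The visible text shows no such draw.

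**Step 5. What could those results influence?** In the final-visit case they arise after 12 weeks of treatment. If 6MWT and KCCQ are done at that visit, the results come too late to affect them. What remains is the "off-line analysis of brachial artery vasodilation using automated edge-detection software" and the phone contact 14 days later.

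**Step 6. With L and M together**, the count given to investigators is 0 in every case, whatever the visit numbering or draw schedule.

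**The case for a change.** The strongest reply is that a start point has no purpose unless earlier results are treated differently, so L does imply an open period. On this view, a reader who reconciles the sentences by ignoring the start point shows that it should go. The missing Flow Chart could fix when Visit 2 falls, but it could not make the two scopes identical. A laboratory working only from the sentence that names it might report early values, and preventing that would cost one sentence.

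Part of this stands. The scopes do differ under every visit numbering, the start point does no useful work, and one wording in both places would be tidier. What does not stand is the step from awkward wording to a defect in the plan. The implied open period is an inference from silence, and an explicit bar elsewhere in the same protocol contradicts it. That a laboratory would follow one sentence and not the other is conjecture: nothing visible shows a reporting instruction of that kind. The case that would matter most, on-treatment results in investigators' hands while outcomes are still being collected, needs an on-treatment draw before the final visit, and no visible text shows one. The Flow Chart's absence from the text supplied for review is not a fault in the plan.

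**Conclusion.** No change to the plan is needed. The two sentences are worded differently but can be met together, and the study-long bar already gives the protection that a correction would aim for. On the laboratory sentence alone, the exposure is 0 on-treatment results, or 120 (144 if all randomized subjects are counted) that arise only at the final visit. With both sentences in force it is 0. No bias in FMD, 6MWT, KCCQ or the marker comparisons is shown, and no analysis would change. The marker comparisons are also declared exploratory.

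This rests on three assumptions: the two sentences cover the same six markers; the marker draws are at baseline and week 12; and site and laboratory follow the protocol as a whole. The counts for the laboratory sentence alone depend on the second assumption, and the Flow Chart would confirm or alter them. The conclusion under both sentences does not depend on it. What remains is a redundant phrase, an editorial matter.
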